#### **1.4.1.4 Human pharmacokinetics and Safety**

In humans, panobinostat exhibits a linear PK profile following i.v. administration. panobinostat exposure is nearly dose- proportional at doses below 60 mg following oral administration; inter-patient variability in exposure (AUC) is 60% with oral and 40% with i.v. panobinostat (coefficient of variability [CV]). The drug has a rapid oral absorption  $T_{max}$  = 1 hour. Absolute bioavailability is 30% and elimination  $t_{1/2}$  is approximately 15 hours.

The clinical development of panobinostat has been conducted with both an i.v. and oral formulation The major dose-limiting-toxicity (DLT) for both formulations administered as a single agent is reversible thrombocytopenia. For the i.v. formulation, a weekly i.v. dosing scheme (Day 1, Day 8 every 21 days) is currently used in clinical studies with thrombocytopenia being managed by dose and schedule adjustment. For the oral formulation, a pooled analysis of data from phase I/II studies indicates that thrombocytopenia is the most common lab abnormality of any grade and of Grade 3-4 in patients treated with the three-times-a-week (TIW), every week (QW) and every-other-week (QOW) schedules. The median time to Grade 3 thrombocytopenia appears to be shorter with the QW dosing as compared with the QOW dosing. The magnitude of platelet count decline is dose-dependent and related to the baseline platelet count. The median time to recovery from severe thrombocytopenia, Grade 3-4 to Grade 2 or below, is approximately 8 days for doses up to 40 mg in solid tumors and lymphomas. The median time to recovery from severe thrombocytopenia is much longer (up to approximately 74 days) for doses up to 60 mg used in hematologic malignancies. Preliminary evidence in patients with solid tumors and lymphomas suggests that switching from the QW to the QOW schedule may be more effective than other dose modifications for reducing the recurrence of thrombocytopenic events

QT prolongation, a known class effect of HDAC inhibitors, appears to be formulation, dose and schedule dependent. For the i.v. formulation, QTcF prolongation of clinical relevance (Grade  $\geq 3$  with absolute increase  $>500$  msec) was seen in 4/15 patients (26.7%)

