**There will be no intra-subject dose escalation.** Decisions regarding dose escalation between cohorts will be guided by the incidence of drug-related dose limiting toxicities (DLTs) occurring within 84 days (12 weeks; through Day 42 of induction cycle 2) of initiation of study therapy. If three patients complete their 84 day period of treatment without DLT, then at least three additional patients must exceed 9 weeks without MTD being reached to be able to dose escalate. This DLT observation interval is based upon inclusion of the known median times to onset of common immune-related adverse events attributed to ipilimumab (see Section 4.3.5.1) and allows for a substantial amount of time for unexpected toxicities with the combined administration of panobinostat and ipilimumab to emerge. Subjects who do not complete the DLT observation period for reasons other than drug-related toxicity will be replaced. One of the following five decisions will be made at the end of the DLT period for each cohort of 3 subjects based on the number of DLT's observed:

- S: stay at the same dose and enroll a cohort of 3 more subjects at that dose
- E: escalate to the next higher dose by enrolling 3 more subjects
- D: de-escalate to the lower dose, and enroll 3 more subjects at the lower dose, or
- DU: declare the current dose as unacceptable and unsafe, de-escalate to the lower dose, and enroll 3 more subjects at the lower dose
- C: Study completed and dose is declared to be the MTD

Decisions S or E are allowed by the design if determined that the corresponding doses are safe based on the target toxicity. Decisions D or U are based on evidence of exceeding predetermined toxicity. With a target toxicity rate of 18%, allowing any dose with estimated  $P_T$  in the (17%, 19%) interval to be selected as the MTD in this study, and with a maximum fixed total of 36 subjects at the dose escalation phase in each arm, the algorithm for dose escalation decisions based on possible total number of subjects at each dose cohort is described in Table 3.2 below.

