**Table 4.1 Dose Escalation regimen for Panobinostat and Ipilimumab**

Dose Cohort	Panobinostat Dose	Ipilimumab Dose
1	5 mg po TIW	3 mg/kg
2	10 mg po TIW	3 mg/kg
3	15 mg po TIW	3 mg/kg
4	20 mg po TIW	3 mg/kg
-1	5 mg po TIW	1 mg/kg

Additional dose levels of panobinostat beyond the 20 mg PO TIW dose cohort may be added as appropriate, although it is expected that all subsequent doses will be no more than 33%

higher than the preceding dose (eg, from 20 mg PO TIW to 25 mg PO TIW). Start of induction cycle 1, Day 1 for the first 3 subjects should be separated by at least 1 day. During the DLT observation (within 84 days of initiation of study therapy), subjects, who for reasons other than study-drug related toxicity, either miss 1 or more of their scheduled doses of ipilimumab, or miss more than 10% of their scheduled Q12 hour doses of panobinostat, or do not complete the first induction cycle, will not be considered evaluable for safety for the purposes of dose escalation and will be replaced.

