##### **B: Non-Hepatic Non-Hematologic DLT**

Any Grade 3 or greater non-hepatic non-hematologic toxicity will be considered as a dose-limiting toxicity with the following specific **exceptions**:

- Grade 3 electrolyte abnormalities that are not complicated by associated clinical adverse experiences, last less than 48 hours and either resolve spontaneously or respond to conventional medical intervention.
- Grade 3 nausea or vomiting that lasts less than 48 hours, and either resolves spontaneously or responds to conventional medical intervention.
- Isolated Grade 3 elevation of amylase or lipase not associated with clinical or radiographic evidence of pancreatitis.
- Isolated Grade 3 fever that lasts  $\leq$  3 days and is not associated with hemodynamic compromise (ie hypotension, clinical or laboratory evidence of impaired end-organ

perfusion).

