Cycle 1 Day 1 dose modification criteria:		
Pre-dose on cycle 1, day 1 3 ECGs separated by at least 5 minutes, obtained prior to panobinostat dosing	Average QTcF > 450 msec	Check and correct the patient's serum potassium, magnesium, calcium and phosphorus immediately, as well as evaluate con-meds. Repeat 3 pre-dose ECGs. If the 3 pre-dose ECGs: Do not meet criteria again, discontinue patient from study. Do meet criteria for dosing; administer study drug treatment.

ECGs to be performed at specified time point	Abnormality Noted	Dose Modification Guideline - At any time during a cycle of therapy (including intended day of dosing)
Cycle 1 Day 5 dose modification criteria		
Pre-dose on cycle 1, day 5: 3 ECGs separated by at least 5 minutes, obtained prior to panobinostat dosing	Average QTcF: ≥ 480 msec to < 500 msec OR > 60 msec increase from baseline average	
Check and correct the patient's serum potassium, magnesium, calcium and phosphorus immediately, as well as evaluate con-meds.
 
Notify Sponsor and transmit to ERT immediately for prompt review.
 
Repeat 3 pre-dose ECGs.
 
If the 3 pre-dose ECGs:
 
Do meet criteria for dosing; administer study drug treatment.
 
Do not meet criteria again, delay dose until the next scheduled time point and repeat 3 pre-dose ECGs.
 
If the repeat 3 pre-dose ECGs:
 
Do not meet pre-dose ECG criteria again, discontinue patient from study.
 
Do meet pre-dose ECG criteria for dosing and QT prolongation is determined to be related to study drug, resume study drug treatment with a dose reduction of one dose level. If however, it was determined that the QT prolongation was secondary to electrolyte abnormalities or con-meds, continue at the same dose level. Repeat ECGs - pre-dose (x3) on the next scheduled dosing day.

	Average QTcF ≥ 500 msec	
Check and correct the patient's serum potassium, magnesium, calcium and phosphorus immediately, as well as evaluate con-meds.
 
Notify Sponsor and transmit to ERT immediately for prompt review.
 
Discontinue patient from study therapy
 
If however, it was determined that the QT prolongation was secondary to electrolyte abnormalities or con-meds: omit dose. On the next scheduled dosing day continue at the same dose level. Repeat ECGs - pre-dose (x3), 3-hours post-dose (x3), on the next scheduled dosing day.

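### A subject removed or dose-reduced in the 84-day window for drug-related toxicity that is not a listed DLT is not replaced and adds nothing to the DLT count, so by the text the subject is scored as treated without a DLT

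*Combined protocol and SAP*

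**What the plan says.** **Who stays in the denominator.** The Synopsis, Section 3.1 and Section 4.2 carry the same rule: "Subjects who do not complete the DLT observation period for reasons other than drug-related toxicity will be replaced". Section 4.3.1 adds an evaluability rule with the same carve-out. Subjects "who for reasons other than study-drug related toxicity, either miss 1 or more of their scheduled doses of ipilimumab", or who breach its panobinostat or first-cycle limits, "will not be considered evaluable for safety for the purposes of dose escalation and will be replaced". Tables 3.2 and 8.1 define N as subjects treated at the dose level, not subjects who completed the window.

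**What enters the numerator.** Section 4.3.3 defines DLTs by the type, grade and duration of drug-related events within 84 days. The general non-hepatic rule is "Any Grade 3 or greater non-hepatic non-hematologic toxicity will be considered as a dose-limiting toxicity", with listed exceptions. No item makes discontinuation, dose reduction or missed doses a DLT.

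**What takes subjects off the assigned dose.** Under Table 4.2, an average QTcF of 480 to <500 msec at Cycle 1 Day 5, or a rise of more than 60 msec, starts a sequence of repeat ECGs. If the finding persists, the instruction is "Do not meet pre-dose ECG criteria again, discontinue patient from study". If it recovers and is judged drug-related, the instruction is "resume study drug treatment with a dose reduction of one dose level". In the Cycle 2 row, repeated QTcF above 480 msec also leads to removal. Section 3.4 separately lets the investigator stop treatment for any adverse event.

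**How the plan grades QTcF.** The sentence in Section 1.4.1.4 that begins "For the i.v. formulation, QTcF prolongation of clinical relevance" links Grade 3 or higher to 500 msec being exceeded.

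**The concern.** The replacement rule and the DLT list do not meet. The replacement rule sets aside exits unrelated to drug toxicity. The DLT list captures events above a severity line. A subject who leaves or is reduced because of drug toxicity below that line falls between them, kept in N with nothing added to the count. No passage gives this subject any other status.

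The DLT count drives every cell of Tables 3.2 and 8.1. The end-of-study MTD estimate described in the Synopsis uses the same observed toxicities. The MTD and RP2D are the primary objective, and Section 1.4.3 names cardiac toxicity as one of panobinostat's two major toxicities. A rule that records incomplete exposure as tolerance pushes the estimate in one direction, toward higher doses.

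**Working it through.** **1. The plan's own figures reproduce.** Section 8.1 says that observed toxicity at the MTD is below 26% for N of 9 or more. The largest acceptable ratios are 2/9 = 22.2% and 3/12 = 25.0%. Escalation is meant to occur below 17%. The highest E cells are 1/6 = 16.7% and 2/12 = 16.7%. The tables are consistent with the stated rule, so the question is what goes into them.

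**2. Timing.** The window is 84 days. Cycle 1 Day 5 is inside it. Cycle 2 Day 1 is study day 42 + 1 = 43, also inside it.

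**3. One cohort of three.** Suppose two subjects are removed or reduced for drug-related QTcF of 480 to <500 msec, and nobody has a listed DLT.
- As written: 0/3, decision E.
- If the two are replaced: one evaluable subject, no decision due.
- If the two count as events: 2/3, decision DU.

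**4. Chance of escalating from a dose.** Let r be the per-subject probability of a counted event. For each cohort of three, b0 = (1−r)³ is the probability of no event and b1 = 3r(1−r)² the probability of exactly one. Under Tables 3.2 and 8.1 there are three routes to E: 0/3; 1/3 then 1/6; and 1/3, 2/6, 2/9, then 2/12. Hence

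P(E) = b0 + b1·b0 + b1²·b0².

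At r = 0.18, b0 = 0.5514 and b1 = 0.3631, so P(E) = 0.5514 + 0.2002 + 0.0401 = 0.792.

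Let p be the listed-DLT rate and q the rate of drug-related removal or reduction without a listed DLT, treated as mutually exclusive. The effective r is p as written, p/(1−q) if such subjects are replaced, and p+q if they count as events. The documents give no value for q, so 5% to 20% is an assumption. The value p = 18% is the plan's target; p = 10% is an assumed lower case.

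| p | q | As written | Replaced | Counted as events |
|---|---|---|---|---|
| 18% | 5% | 79.2% | 77.1% | 67.8% |
| 18% | 10% | 79.2% | 74.7% | 56.2% |
| 18% | 15% | 79.2% | 72.0% | 45.2% |
| 18% | 20% | 79.2% | 69.0% | 35.4% |
| 10% | 5% | 93.8% | 93.0% | 85.4% |
| 10% | 20% | 93.8% | 89.9% | 51.7% |

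**5. How often it would arise.** The chance of at least one such subject is 1 − (1−q)^n. For q from 5% to 20% this is 14.3% to 48.8% in three subjects and 26.5% to 73.8% in six.

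These figures apply the decision tables alone and ignore the additional completion condition in Section 3.1, taken up below.

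**The case against.** **Section 3.1 has a further condition.** After three patients complete 84 days of treatment without a DLT, at least three more must pass 9 weeks before escalation. A reader might infer from the tables that a whole cohort of three could leave for QTcF in the second week and the dose would simply go up. Section 3.1 does not support that, because removed subjects have not completed 84 days. This part of the objection stands. However, the condition conflicts with E at 0/3 in the tables, gives removed subjects no status, and does not reach a dose-reduced subject who finishes 84 days.

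**The scoring is inferred.** No sentence says that these subjects are DLT-free. It follows from the definition of N, the replacement carve-out and silence elsewhere. That is correct, and the point claims no more.

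**A severity-based DLT definition is deliberate.** Section 1.4.4 argues for the target from Grade 3 or higher toxicity rates. A reader might take the fall from 79.2% to as low as 35.4% as the bias in the plan. It is not. That column widens the event definition while keeping rules built for 18%, so lower escalation follows by construction. The replacement column keeps the plan's definition and shows a much smaller effect.

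**QTcF may seldom trigger this.** Section 1.4.1.4 reports QTcF above 500 msec in 6 of 635 patients (0.9%) on intermittent oral dosing, and Day 5 removal needs repeated failures. That is a fair caution about frequency, but the figure does not cover the 480 to <500 msec or >60 msec triggers.

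**Scope.** Not every event below Grade 3 escapes the DLT list, since Section 4.3.3.1 counts certain Grade 2 eye events. The documents do not grade a rise of more than 60 msec. The Day 1 row of Table 4.2 is pre-dose and does not apply, and values above 500 msec would be DLTs if drug-related. Outside Table 4.2, the reductions in Section 4.3.6 are triggered mainly by DLTs. The gap does extend to Grade 3 thrombocytopenia without clinically significant bleeding, which Section 4.3.3.2 does not list, if it leads the investigator to stop treatment.

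**Oversight.** Escalation is guided by DLT incidence rather than automatic, and the DMC in Section 7 reviews aggregate data. It is advisory, and neither provision says how to score the subject.

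**Conclusion.** The gap holds on the text. Subjects removed or reduced inside the window for drug-related toxicity that is not a listed DLT stay in N and add nothing to the count, and Table 4.2 produces them by rule. The direction is toward understating the DLT rate and favouring escalation.

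The size cannot be fixed from the documents. At an 18% DLT rate and assumed rates of 5% to 20%, escalation from a dose is 79.2% likely as written. Replacing these subjects lowers this by 2.1 to 10.2 points; counting them as events lowers it by 11.4 to 43.8 points. The first range is the fairer measure under the plan's own DLT definition. The figures also assume independent subjects and the decision tables applied alone. The documents do not support the stronger conclusion that any-grade toxicity leading to a reduction must be a DLT.

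**What to change.** Reconcile Section 4.3.3, Table 4.2, the replacement and evaluability rules (Synopsis, Sections 3.1, 4.2 and 4.3.1), the completion condition in Section 3.1, and Tables 3.2 and 8.1. Before further escalation, add one sentence: a subject removed or dose-reduced within the DLT window for study-drug-related toxicity that is not a listed DLT may not be scored as a DLT-free evaluable subject at the assigned dose.

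The investigators should decide in advance whether such a subject is replaced or counted as an event. If counted, the 18% target should be rechecked against the wider definition. No QTcF threshold or dose rule needs to change.

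The cost is a short amendment. Some escalation decisions will come later or need replacement subjects.

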**Table 3.2 Dose Escalation Algorithm for each arm: modified TPI design**

Dose Escalation: This is a Phase I dose escalation trial and the sample size at each dose depends on the observed toxicity, and a total of 36 subjects at the dose-escalation phase allows sufficient number of subjects if needed, e.g. more than 6 subjects if dose-limiting toxicities are observed among 2 of 6 subjects, to better estimate the toxicity rates per dose, and more accurately determine the MTD. Cohorts of 3 subjects with possible expansions to 6, 9, or 12 subjects will be treated at each suggested dose level until MTD is defined.

In this protocol, we will be using a new phase I trial approach (Table 3.2), modified from a design from Ji et al. This approach provides a broader phase I experience than the traditional 3+3 design, thus allowing for a more robust choice of an MTD. While setting the target toxicity rate at 18%, this design allows further examination of a dose when 2 DLTs occur among 6 patients, while still keeping the observed toxicity at the MTD well managed (it is below 26% for sample sizes  $\geq 9$ ). Moreover the MTD will exploit the isotonic nature of dose escalation in determination of the MTD.

**Table 3.2 Decision Rules on dose escalation based on number of DLTs\*\***

N*	Observed DLTs per cohort and treatment decisions									
	0	1	2	3	4	5	6			
3	E	S	DU	DU	-	-	-	-	-	-
6	E	E	S	DU						
9	E	E	S	D	DU	DU	DU	DU	DU	DU
12	E	E	E	C	DU	DU	DU	DU	DU	DU

N\* =number of subjects treated at a given dose level

- S: stay at the same dose and enroll a cohort of 3 more subjects at that dose
- E: escalate to the next higher dose by enrolling 3 more subjects
- D: de-escalate to the lower dose, and enroll 3 more subjects at the lower dose, or
- DU: declare the current dose as unacceptable and unsafe, de-escalate to the lower dose, and enroll 3 more subjects at the lower dose
- C: Study completed and dose is declared to be the MTD

\*\*for MTD target toxicity  $p_T=18\%$ , and allowing any dose with  $p_T$  in (17%, 19%) to be selected. The modifications involve escalating the dose whenever the observed toxicity rate is below 17% and using the N-1st patient to define the change when the toxicity rate exceeds 19% and  $N \geq 9$  to account for the fact that the design is being used in cohorts of 3 rather than continuously as

designed by Ji et al.

Based on the above design, escalation to the next higher dose level can occur if DLT's are observed in 0 of 3 or 6 subjects, in up to 1 of 6 subjects, in up to 2 of 12 subjects, and so on. If DLTs are observed in a greater number of subjects and escalation is not yet permitted, additional subjects in cohorts of 3 will be enrolled at the same dose in order to better estimate the true DLT rate at that dose until either escalation is allowed, the dose is deemed unacceptable and should not be used, or de-escalation is recommended, based on Table 3.2. All available clinical and laboratory data, and the nature, time of onset and time to resolution of DLTs observed during dose escalation will be reviewed to determine whether an alternate dose schedule should be examined after consultation between the Principal Investigator and the Data Monitoring Committee (DMC) if needed. If agreed upon, the alternate schedule will be identified by a protocol amendment and the MTD determined for the revised dose schedule.

This phase I study design has tended to be applied to a fixed sample size of 30. Due to the increased complexity of this combination-dose trial, we have chosen a sample size of 36.

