Note that decisions S or E are allowed by the design when determined that the corresponding doses are safe based on the target toxicity. Decisions D or DU are based on evidence of exceeding predetermined toxicity. With a target toxicity rate of 18%, allowing any dose with estimated  $P_T$  in the (17%, 19%) interval to be selected as the MTD in this study, and with a maximum fixed total of 12 subjects at the dose escalation phase in each arm, the algorithm for dose escalation decisions based on possible total number of subjects at each dose cohort is described in Table 3.2.

Based on the above design, escalation to the next higher dose level can occur if DLTs are observed in 0 of 3 or 1 of 6 subjects, in up to 2 of 12 subjects, and so on. If DLTs are observed in a greater number of subjects and escalation is not yet permitted, additional subjects in cohorts of 3 will be enrolled at the same dose in order to better estimate the true DLT rate at that dose until either the dose is deemed safe and an escalation is allowed, the dose is deemed unacceptable and should not be used, or de-escalation is recommended, based on decision rules outlined in Table 3.2. At the end of the dose escalation phase, the MTD will be estimated by isotonic regression or another Bayesian model-based approach (eg logistic regression) using observed toxicities at all studied doses.

The combination dose with posterior probability of toxicity closest to the target toxicity,  $P_T$ , will be declared as the MTD.

The dose escalation plan (see table above) uses a modified  $J_i$  design, with dose escalation decisions made every three patients. The trial will enroll 36 patients for determination of the MTD, but will be successfully concluded earlier if 12 patients are accrued at the dose determined to be the MTD, with at most 3 toxicities.

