## 8 STATISTICAL CONSIDERATIONS

### 8.1 Sample Size Determination

Dose Escalation: This is a Phase I dose escalation trial and the sample size at each dose depends on the observed toxicity; however a total of 36 subjects for the dose-escalation study allows sufficient number of subjects if needed, e.g. more than 6 subjects if dose-limiting toxicities are observed among 2 of 6 subjects, to better estimate the toxicity rates per dose, and more accurately determine the MTD. Cohorts of 3 subjects with expansions to 6, or possibly even 9 or 12 subjects will be treated at each suggested dose level until MTD is determined.

In this protocol, we will be using a new phase I trial approach (Table 8.1), modified from a design from Ji et al. This approach provides a broader phase I experience than the traditional 3+3 design, thus allowing for a more robust choice of an MTD. While setting the target toxicity rate at 18%, this design allows further examination of a dose when 2 DLTs occur among 6 patients, while still keeping the observed toxicity at the MTD well managed (it is below 26% for sample sizes  $\geq 9$ ). The trials will enroll up to 36 patients for determination of the MTD, but will be successfully concluded earlier if 12 patients are accrued at the dose determined to be the MTD, with 3 DLTs. If, at any time, one de-escalates to a dose which has already accrued 12 patients, the study will be terminated and that dose declared to be the MTD. The MTD is obtained at 33 patients if 9 or 12 patients have been accrued at the current dose and the dose is acceptable (E, S or C). Otherwise, if the current dose has  $\leq 1$  of 3, or  $\leq 2$  of 6 DLTs, then three more patients will be accrued at that dose – if at most 1 of 6, or 2 of 9 have DLTs, that dose is the MTD.

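### Tables 3.2 and 8.1 give no usable action for E when the next higher dose has already been declared DU, and the 12-patient stop is worded in two ways

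*Combined protocol and SAP*

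**What the plan says.** Tables 3.2 and 8.1 use the same codes. By number treated, they give:

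- N = 3: 0 DLTs E, 1 S, 2 or more DU.
- N = 6: 0 or 1 E, 2 S, 3 or more DU.
- N = 9: 0 or 1 E, 2 S, 3 D, 4 or more DU.
- N = 12: 0 to 2 E, 3 C, 4 or more DU.

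E is "E: escalate to the next higher dose by enrolling 3 more subjects". DU is "DU: declare the current dose as unacceptable and unsafe, de-escalate to the lower dose, and enroll 3 more subjects at the lower dose". The text after Table 3.2, like the Synopsis, describes the DU outcome as one where "the dose is deemed unacceptable and should not be used".

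Two sentences qualify E. The Synopsis says that "decisions S or E are allowed by the design when determined that the corresponding doses are safe". Section 3.1 says "Decisions S or E are allowed by the design if determined that the corresponding doses are safe based on the target toxicity". The introduction to Table 3.2 adds that cohorts of 3 "with possible expansions to 6, 9, or 12 subjects will be treated at each suggested dose level until MTD is defined".

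On early stopping, the Synopsis requires that "12 patients are accrued at the dose determined to be the MTD, with at most 3 toxicities"; Section 8.1 requires that "12 patients are accrued at the dose determined to be the MTD, with 3 DLTs". Section 8.1 also ends the study on de-escalation to a dose that already has 12 patients, and has a separate rule from 33 patients on.

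**The concern.** DU always sends the next 3 patients to the dose below, so a later E at that lower dose is a normal outcome. The table then names the DU dose as the next assignment, while the surrounding text says not to use it. The study team would have to decide, with DLT data in hand, whether to stay, fill to 12 or stop. This is the assignment rule for the primary objective (MTD and RP2D), so the step should be fixed in advance.

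The two wordings of the 12-patient stop add to this. At 0, 1 or 2 DLTs in 12, the table says E and Section 8.1 does not stop, but the Synopsis does.

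**Working it through.** **The plan's own figure.** Sections 3.1 and 8.1 put observed toxicity at the MTD below 26% for 9 or more patients. The highest accepted rates are 2/9 = 22.2% and 3/12 = 25.0%, so the figure reproduces.

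**Shortest route to the conflict.** Dose 1 at 0/3 (E); dose 2 at 2/3 (DU); dose 1 at 0/6 or 1/6 (E, into the DU dose). That is 9 patients. Checking each rule that might supply the next step:

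- C needs 3/12.
- The Synopsis stop needs 12 patients at the dose.
- The 8.1 de-escalation stop needs 12 already at the lower dose.
- The other 8.1 rule starts at 33 patients.
- The dropping rule under De-escalation in the Synopsis covers only cohorts 1 and -1.
- The DMC (Section 7) is advisory.
- The end-of-escalation isotonic or Bayesian estimate selects a dose; it does not assign the next cohort.

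**How often, doses 1 and 2 alone.** The true rates are assumptions. The only anchors are 8.1% for ipilimumab 3 mg/kg (Section 1.1.1) and under 5% for panobinostat (Section 1.4.4). Table 8.1 was enumerated exactly in cohorts of 3, stopping at 12 with at most 3 DLTs:

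P(conflict) = P(dose 1 exits by E) × P(dose 2 goes DU on first pass) × P(dose 1, resumed with its own data, exits by E again).

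For 8%/10%:

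- Dose 1 exits by E at 0/3, or at 1/3 then 0/3: 0.92³ + 3(0.08)(0.92²)(0.92³) = 0.779 + 0.158 = 0.937.
- Dose 2 goes DU: 0.0280 at N = 3, 0.0068 at 6, 0.0017 at 9, 0.0012 at 12; total 0.0377.
- Dose 1 exits by E again: 0.947.
- Product: 0.937 × 0.0377 × 0.947 = 0.033.

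Section 3.1 also has a sentence that can be read as requiring 6 patients after 0/3 before escalation. Both readings are shown.

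| Rates, dose 1/dose 2 | 0/3 escalates | 6 needed first |
|---|---|---|
| 8/10% | 3.3% | 3.3% |
| 8/13% | 5.9% | 5.9% |
| 12/18% | 10.5% | 10.1% |
| 18/25% | 16.1% | 14.0% |
| 10/25% | 21.9% | 21.8% |
| 15/30% | 25.7% | 23.7% |
| 10/40% | 48.9% | 48.4% |

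**All four doses.** Simulation used 100,000 trials per scenario, applied the 33-patient rule, added no dose above 20 mg, and ended the path on a drop to cohort -1.

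| Rates, doses 1 to 4 | 0/3 escalates | 6 needed first |
|---|---|---|
| 5/8/10/13% | 13% | 10% |
| 8/10/13/18% | 22% | 16% |
| 8/13/18/25% | 36% | 25% |
| 12/18/25/32% | 45% | 31% |

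On the first reading, the first conflict comes at a median of 15 to 18 patients, well before 33.

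**Does the improvised choice matter?** Take the lower dose at a true 30%, given that the upper dose is DU. With cohort probabilities 0.343, 0.441, 0.189 and 0.027 for 0, 1, 2 and 3 DLTs, the second E is reached at:

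- 0/6: 0.343 × 0.343 = 0.1176
- 1/6: 0.343 × 0.441 = 0.1513
- 1/9 (1/3, then 1/6, then 1/9): 0.441 × 0.343 × 0.343 = 0.0519

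Stopping there accepts the dose with probability 0.321. Filling to 12 under the table succeeds with probability 0.920 from 0/6, 0.680 from 1/6 and 0.973 from 1/9. This gives 0.1176 × 0.920 + 0.1513 × 0.680 + 0.0519 × 0.973 = 0.262.

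| True rate of lower dose | Stop at second E | Fill to 12 |
|---|---|---|
| 25% | 43.1% | 38.1% |
| 30% | 32.1% | 26.2% |
| 33% | 26.4% | 20.2% |

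If 6 patients are needed before escalation, the second E comes only at 0/9 or 1/9. From 0/9 the fill cannot fail; from 1/9 it fails only on 3/3, which is 0.3³ = 2.7% at a true 30%. The two choices then nearly coincide.

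**The case against.** The strongest reply is that the text already bars re-entry. A DU dose is not to be used, and E is allowed only when the doses concerned are safe. With the upper dose barred, expansion to 6, 9 or 12 and the Synopsis stop at 12 point to filling the lower dose, and no provision permits stopping at 6 before 33 patients. This largely stands: a careful team would probably fill to 12. What it does not supply is a sentence that replaces E. The intended step has to be inferred, and the stop it relies on is worded differently in Section 8.1.

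A reader might infer that the protocol directs patients back to an unsafe dose, and count the conflict frequencies as patient exposure. The documents do not support that. The frequencies show how often two statements collide.

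A reader might also compare the plain chance of at most 1 DLT in 6 with the chance of also passing the fill to 12. That overstates the stakes. A dose that goes 1/3 then 1/6 has 6 patients when it escalates and 9 when it returns to E, so stopping at 6 is not on offer there. Nor is acceptance under the table the only MTD rule, since the Synopsis selects by a model over all doses studied.

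**Conclusion.** The conflict holds as a matter of text, whatever rates are assumed: E is defined without exception, and no rule gives the substitute step before 33 patients. The Synopsis and Section 8.1 also disagree on 0 to 2 DLTs in 12.

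Its frequency depends on assumed DLT rates: 3% to 6% for doses 1 and 2 near the component anchors, 10% to 49% at higher or steeper rates, and 13% to 45% over four doses (10% to 31% if 6 patients are needed before escalation). The component anchors are not combination DLT rates, so none of these is a prediction.

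The consequence is modest. Stopping instead of filling raises the chance of accepting a dose truly at 25% to 33% by about 5 to 6 percentage points, and by far less on the 6-patient reading. Severity is minor to moderate.

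A smaller related gap lies in the cohort 1/-1 alternation in the Synopsis. With cohort 1 at 2/3 (DU) and cohort -1 at 1/3 (S), the difference is 1, so cohort 1 would reopen. This may be deliberate, since the Synopsis calls the relative toxicity of the two cohorts unclear, but it does not say so.

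**What to change.** Add a footnote to Tables 3.2 and 8.1, with matching text in the Synopsis, Section 3.1 and Section 8.1:

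1. A dose declared DU, and every higher dose, is closed to enrolment and cannot be the MTD.
2. E immediately below a closed dose is treated as S until that dose has 12 patients.
3. At 12 patients with at most 3 DLTs the study stops and that dose is the MTD. Section 8.1 is aligned to at most 3.

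As a secondary change, state under De-escalation in the Synopsis whether a cohort 1 declared DU may be re-entered by alternation.

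The cost is wording only, and the 36-patient cap holds. In the four-dose simulations in which 0/3 escalates, trials that meet the conflict end at a mean of 22 to 23 patients under these rules. The downside is that a dose truly at 18% is closed by chance on first pass with probability 0.0855 + 0.0311 + 0.0113 + 0.0062 = 13.4% (DU at N = 3, 6, 9 and 12), which DU already implies.
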